## 5.5 Telephone Calls (Weeks 1, 2 and 3)

The patient and/or legal representative must be contacted by telephone weekly (every 7 ± 3 days) on Weeks 1, 2 and 3 to ensure that the titration of dose or treatment is proceeding satisfactorily.

If the patient appears to be having difficulty with the treatment, patient and/or legal representative should be contacted again, as frequently as necessary.

Remind the patient/legal representative that if treatment is stopped early, patient must return to the clinic for an Early Termination Visit as soon as possible, but no later than 1 month following treatment discontinuation.

Remind patients to interrupt therapy immediately if they develop an infection. Patients must be advised to report promptly to the Investigator any symptoms indicative of infection such as fever, sore throat, or flu-like symptoms. In presence of confirmed fever and/or infection, they will be required to have their neutrophil counts tested as soon as possible and no later than 24 hours after the symptoms of infection are detected.

All telephone contacts must be fully documented as follows:

- Record date and time of contact;
- Record name of person contacted (patients, parent, legal representative);
- Remind the patient and/or legal representative of the study medication dose and instructions on how to take medication;
- Record any adverse events
- Note if the patient has used any concomitant medications. If so, document them as specified in [Sections 8.2.4.3, 8.2.4.8, and 8.2.1](#);
- Remind patient to visit the site or a local laboratory for the weekly blood draws;
- Reconfirm the next study visit;
- Include the name and signature of the person contacting the patient.

## 5.6 Monthly Visits (Weeks 4, 8, 16, 20, 32, 36, 44 and 48 Visits)

Weeks 4, 8, 16, 20, 32, 36, 44 and 48 visits assessments will consist of the following procedures. Each visit could occur between -7 or +7 days from the indicated visit day.

- Take vital signs and weight;
- Collect blood sample for hematology and biochemistry;
- Collect blood sample for pregnancy testing for all females of childbearing potential. A negative result will be required for study continuation;
- Review patient diary card with the patient, and/or if applicable patient's authorized legal representative, then collect and file the diary card with the source documents; provide new diary card, and remind patient how to complete the diary card.
- Determine if patient has had any AEs or SAEs or used any concomitant medications. If so, document them as specified in [Sections 6.3](#) and [8.2.4](#);
- Conduct contraceptive counselling for all sexually active patients;
- Collect and account for the medication dispensed at the previous applicable visit;
- Verify/adjust dose level, according to recommendations;
- Dispense the study medication as per [Section 7.4](#);
- Instruct the patient, and/or if applicable patient's authorized legal representative, how to take the medication;
- Remind the patient, and/or if applicable patient's authorized legal representative, that all used and unused medication bottles must be returned at the next monthly, quarterly or semi-annual study visit;
- Provide a new patient diary card and explain how to complete it;
- Remind the patient, and/or if applicable patient's authorized legal representative, that she/he must carefully keep track of adverse events and medication used to treat them as well as any other medication taken;
- Remind the patient, and/or if applicable patient's authorized legal representative, that if study medication is stopped early, she/he must return to the clinic for an Early Termination Visit as soon as possible, but no later than 4 weeks following study medication discontinuation;
- Remind patient, and/or if applicable patient's authorized legal representative, if an infection develops, therapy must be interrupted immediately. Patients should be advised to report immediately to their physician any symptoms indicative of infection such as fever, sore throat, and flu-like symptoms. In presence of confirmed fever and/or infection, they will be required to have their neutrophil counts tested as soon as possible and no later than 24 hours after the symptoms of infection are detected;
- If the patient is receiving a blood transfusion during this visit or has received blood transfusions since the last visit (except for those patients who received an emergency transfusion), record the type of transfusion (simple, exchange, partial exchange), volume of blood that the patient received during the transfusions, and

the mean hematocrit of the packed red blood cell units transfused (data obtained from the site's blood bank);

- Remind patient to visit the site or a local laboratory for the weekly (applicable at Weeks 4, 8, 16, and 20) or biweekly (applicable at Weeks 32, 36, 44, and 48) blood draws;
- Schedule next study visit.

## 5.7 Quarterly Visits (Weeks 12 and 40 Visits)

Weeks 12 and 40 visits assessments will consist of the following procedures. Each visit could occur between -7 and +7 days from the indicated visit day.

- Take vital signs and weight;
- Collect blood sample for serum ferritin, hematology and biochemistry;
- Collect blood sample for pregnancy testing for all females of childbearing potential. A negative result will be required for study continuation;
- Review patient diary card with the patient, and/or if applicable patient's authorized legal representative, then collect and file the diary cards with the source documents; provide new diary card, and remind patient how to complete the diary card.
- Determine if patient has had any AEs or SAEs or used any concomitant medications. If so, document them as specified in [Sections 6.3](#) and [8.2.4](#);
- Conduct contraceptive counselling for all sexually active patients;
- Collect and account for the medication dispensed at the previous applicable visit;
- Verify/adjust dose level, according to recommendations;
- Dispense the study medication as per [Section 7.4](#);
- Instruct the patient, and/or if applicable patient's authorized legal representative, how to take the medication;
- Remind the patient, and/or if applicable patient's authorized legal representative, that all used and unused medication bottles must be returned at the next monthly or semi-annual study visit;
- Provide a new patient diary card and explain how to complete it;
- Remind the patient, and/or if applicable patient's authorized legal representative, that she/he must carefully keep track of adverse events and medication used to treat them as well as any other medication taken;
- Remind the patient, and/or if applicable patient's authorized legal representative, that if study medication is stopped early, she/he must return to the clinic for an Early Termination Visit as soon as possible, but no later than 4 weeks following study medication discontinuation;

- Remind patient, and/or if applicable patient's authorized legal representative, that if an infection develops, therapy must be interrupted immediately. Patients should be advised to report immediately to their physician any symptoms indicative of infection such as fever, sore throat, and flu-like symptoms. In presence of confirmed fever and/or infection, they will be required to have their neutrophil counts tested as soon as possible and no later than 24 hours after the symptoms of infection are detected;
- If the patient is receiving a blood transfusion during this visit or has received blood transfusions since the last visit (except for those patients who received an emergency transfusion), record the type of transfusion (simple, exchange, partial exchange), volume of blood that the patient received during the transfusions, and the mean hematocrit of the packed red blood cell units transfused (data obtained from the site's blood bank);
- Remind patient to visit the site or a local laboratory for the weekly (applicable at Week 12) or biweekly (applicable at Week 40) blood draws;
- Schedule next study visit.

## 5.8 Semi-Annual Visit (Week 26 Visit)

Week 26 visits assessments will consist of the following procedures. This visit should occur between -7 and +7 days from the indicated visit day.

- Perform physical examination;
- Take vital signs (including weight and height);
- Collect blood sample for serum ferritin, hematology, biochemistry and serology;
- Collect blood sample for pregnancy testing for all females of childbearing potential. A negative result will be required for study continuation;
- Collect urine for urinalysis;
- Perform 12-lead ECG;
- Perform MRI scan for:
  - Liver, and transmit to a central laboratory for interpretation and LIC calculation;
  - Cardiac MRI T2\*, and transmit to a central laboratory for interpretation;
- Complete patient-reported quality of life questionnaire (SF-36 or Child Health Questionnaire);
- Review patient diary card with the patient, and/or if applicable patient's authorized legal representative; then collect and file the diary card with the source documents, provide new diary card, and remind patient how to complete the diary card.

- Determine if patient has had any AEs or SAEs or used any concomitant medications. If so, document them as specified in [Sections 6.3](#) and [8.2.4](#);
- Receive and account for the medication dispensed at the previous applicable visit;
- Conduct contraceptive counselling for all sexually active patients;
- Verify/adjust dose level, according to recommendations;
- Dispense the study medication as per [Section 7.4](#);
- Instruct the patient, and/or if applicable patient's authorized legal representative, how to take the medication;
- Remind the patient, and/or if applicable patient's authorized legal representative, that all used and unused medication bottles must be returned at the next monthly or quarterly study visit;
- Provide a new patient diary card and explain how to complete it;
- Remind the patient, and/or if applicable patient's authorized legal representative, that she/he must carefully keep track of adverse events and medication used to treat them as well as any other medication taken;
- Remind the patient, and/or if applicable patient's authorized legal representative, that if study medication is stopped early, she/he must return to the clinic for an Early Termination Visit as soon as possible, but no later than 4 weeks following study medication discontinuation;
- Remind patient, and/or if applicable patient's authorized legal representative, that if an infection develops, therapy must be interrupted immediately. Patients should be advised to report immediately to their physician any symptoms indicative of infection such as fever, sore throat, and flu-like symptoms. In presence of confirmed fever and/or infection, they will be required to have their neutrophil counts tested as soon as possible and no later than 24 hours after the symptoms of infection are detected;
- If the patient is receiving a blood transfusion during this visit or has received blood transfusions since the last visit (except for those patients who received an emergency transfusion), record the type of transfusion (simple, exchange, partial exchange), volume of blood that the patient received during the transfusions, and the mean hematocrit of the packed red blood cell units transfused (data obtained from the site's blood bank);
- Remind patient to visit the site or a local laboratory for the biweekly blood draws;
- Schedule next study visit.

## 5.9 End of Study Visit (Week 52 or Early Termination Visit)

The End of Study assessment (at 52 weeks  $\pm$  7 days from the start of study medication) or Early Termination will consist of the following procedures:

- Perform physical examination;
- Review medical history and concurrent medications;
- Take vital signs, weight, and height;
- Collect blood sample for serum ferritin, hematology, biochemistry (fasting glucose; patient must come to the site following a 10-hour fast), and serology;
- Collect blood sample for pregnancy testing for all females of childbearing potential;
- Collect urine for urinalysis;
- Perform 12-lead ECG;
- Perform MRI scan for:
  - Liver, and transmit to a central laboratory for interpretation and LIC calculation;
  - Cardiac MRI T2\* and transmit to a central laboratory for interpretation;
- Complete patient-reported quality of life questionnaire (SF-36 or Child Health Questionnaire);
- Review patient diary card with the patient, and/or if applicable patient's authorized legal representative, then collect and file the diary card with the source documents;
- Determine if patient has had any AEs or SAEs or used any concomitant medications. If so, document them as specified in [Sections 6.3](#) and [8.2.4](#);
- If the patient has received blood transfusions since the last visit (except for those patients who received an emergency transfusion), record the type of transfusion (simple, exchange, partial exchange), volume of blood that the patient received during the transfusions, and the mean hematocrit of the packed red blood cell units transfused (data obtained from the site's blood bank);
- Collect and account for the medication dispensed at the previous applicable visit;
- Explain to the patient, and/or if applicable the patient's authorized legal representative, that she or he should inform the site if she/he experiences any serious medical problems (SAEs) in the 30 days following the last dose;
- Follow up on any continuing adverse events or serious adverse events until resolution, until the condition stabilizes, until the event is otherwise explained, or until the patient is lost to follow-up.

## 5.10 Early Termination

Patients can be withdrawn from the study at any time. Reasons for withdrawal will be documented in the source document and eCRF, and early termination visit procedures should be performed within 1 month.

These data should be recorded and entered in the eCRF, as they constitute essential data from an evaluation that should be conducted prior to discharging any patient from the study.

## 6 TREATMENT

### 6.1 Study Medication

The treatment phase of the study will last 52 weeks, beginning on the day of the first dose of the study medication. Dispense the study medication as per [Section 7.4](#). As per Section 4.6.5 and 4.6.6 of the ICH Consolidated Guideline on GCP, the Investigator is responsible for ensuring that the investigational products are used only in accordance with the approved protocol, that the correct use of the medication has been clearly explained by the Investigator or delegate to each patient, and that the patient continues to take the medication according to those instructions throughout the trial.

#### **Deferiprone treatment arm:**

During the study, patients will be prescribed Ferriprox 500 mg tablets or deferiprone 80 mg/mL oral solution, according to patient preference or product's availability, for administration three times a day (tid). The dose of deferiprone will be based on the transfusional iron input and the severity of iron load at baseline, and may be adjusted on the basis of the magnitude of change in iron overload during the study.

#### Deferiprone 25 mg/kg tid:

Patients with transfusional iron input  $\leq 0.3$  mg/kg/day in the 3 months prior to baseline

**AND**

Patients with a baseline measure of iron load of:

- Serum ferritin  $<2500$   $\mu$ g/L

**AND**

- LIC  $<15$  mg/g dry weight

**AND**

- Cardiac T2\*  $> 20$  ms

#### Deferiprone 33 mg/kg tid:

Patients with a transfusional iron input  $> 0.3$  mg/kg/day in the 3 months prior to baseline

**OR**

Patients with at least one baseline measure of iron load as follows:

- Serum ferritin  $\geq 2500 \mu\text{g/L}$

**OR**

- LIC  $\geq 15 \text{ mg/g dry weight}$

**OR**

- Cardiac T2\*  $\leq 20 \text{ ms}$

Dosing of all patients will be initially at 15 mg/kg tid for 1 week, which will be increased to 20 mg/kg tid in Week 2 and to 25 mg/kg tid in Week 3, which will be the treatment dose for the remainder of the trial, unless a patient meets the 33 mg/kg tid dosing criteria. In that case, the dose of deferiprone will be increased further to 33 mg/kg tid in Week 4 and this dose will be the treatment dose for the remainder of the trial.

The dose of deferiprone will also be increased to 33 mg/kg tid at any time during the trial if the mean daily transfusional iron input increases to more than 0.3 mg/kg body weight for at least 3 consecutive months OR at Week 26 if there is less than 10% improvement from baseline to Week 26 in at least one of the measures indicative of iron overload (serum ferritin, cardiac MRI T2\* or LIC).

Dose reduction recommendations will be based on regular assessment of safety markers for adverse reactions that are possibly dose dependent, such as gastrointestinal upset, increases in serum liver enzyme levels, and arthropathies.

### **Deferoxamine treatment arm:**

During the study, patients will be prescribed deferoxamine as per the approved US prescribing information at doses of 20 – 40 mg/kg/day for children (<16 years of age) and 40–50 mg/kg/day in adults ( $\geq 16$  years of age) as 8 – 12 h subcutaneous infusion for 5 – 7 days per week. The dose of deferoxamine will be based on the transfusional iron input, on the severity of iron load at baseline, and on the magnitude of its change during the study.

#### **Deferoxamine 20 mg/kg/day (children) or 40 mg/kg/day (adults):**

Patients with transfusional iron input  $\leq 0.3 \text{ mg/kg/day}$  in the 3 months prior to baseline

**AND**

Patients with a baseline measure of iron load of:

- Serum ferritin  $< 2500 \mu\text{g/L} *$

**AND**

- LIC  $< 15 \text{ mg/g dry weight}$

**AND**

- Cardiac T2\*  $> 20 \text{ ms}$

- \* If there is a delay in obtaining the results of the baseline serum ferritin assessment from the central laboratory, the most recent result (obtained within the last 3 months) should be used to calculate the starting DFO dosage. This dosage must remain in effect until the baseline serum ferritin results become available, at which time it is to be adjusted if necessary. If no serum ferritin measure has been obtained within the last 3 months, the start of dosing must be deferred until the baseline results are available.

**Deferoxamine up to 40 mg/kg/day (children) or 50 mg/kg/day (adults):**

Patients with a transfusional iron input  $> 0.3 \text{ mg/kg/day}$  in the 3 months prior to baseline

**OR**

Patients with at least one baseline measure of iron load as follows:

- Serum ferritin  $\geq 2500 \text{ }\mu\text{g/L}$

**OR**

- LIC  $\geq 15 \text{ mg/g dry weight}$

**OR**

- Cardiac T2\*  $\leq 20 \text{ ms}$

*Children (<16 years of age)*

The dose of deferoxamine will also be increased up to 40 mg/kg for 5 – 7 days per week at any time during the trial if the mean daily transfusional iron input increases to more than 0.3 mg/kg body weight for at least 3 consecutive months OR at Week 26 if there is less than 10% improvement from baseline to Week 26 in at least one of the measures of iron overload (serum ferritin, cardiac MRI T2\* or LIC).

*Adults ( $\geq 16$  years of age)*

The dose of deferoxamine will be increased up to 50 mg/kg for 5 – 7 days per week at any time during the trial if the mean daily transfusional iron input increases to more than 0.3 mg/kg body weight for at least 3 consecutive months OR at Week 26 if there is less than 10% improvement from baseline to Week 26 in at least one of the measures of iron overload (serum ferritin, cardiac MRI T2\* or LIC).

Dose reduction recommendations will be based on regular assessment of safety markers.

## 6.2 Rationale for Selection of Doses

Deferiprone:

In thalassemia syndromes, the dose of 25 to 33 mg/kg body weight three times a day for a total daily dose of 75 to 99 mg/kg, seven days a week, has been approved on the basis

that it is able to reduce or control transfusional iron burden. The transfusion regimen in SCD patients in this study is similar to that employed in patients with thalassemia major, and as such, is expected to be capable of offsetting iron accumulation in the majority of transfusion-dependent patients (Bansal RK. 2002; Longo F *et al.* 1999; Pennell DJ *et al.* 2006; Piga A *et al.* 2003; Rombos Y *et al.* 2000; Taher A *et al.* 2005; Wonke B *et al.* 1998). The recommended initial dose of deferiprone is 25 mg/kg, orally, three times per day for a total of 75 mg/kg/day. The maximum dose is 33 mg/kg, three times per day for a total of 99 mg/kg/day.

#### Deferoxamine:

Initial and maximal doses recommendations for deferoxamine are based on its prescribing information.

### **6.3 Prior and Concomitant Medications**

All medications taken during the 3 months prior to dosing up to the end of the study (Week 52 or early termination) will be recorded and reviewed by the Investigator.

Medications considered necessary for the patient's welfare may be given at the discretion of the Investigator. The administration of all medications (including study product, herbal medications, and over-the-counter medications) and nutrition supplements must be recorded in the source document and the appropriate sections of the eCRF. During treatment with deferiprone, patients **must not** receive any other investigational product or any drugs that are known to cause neutropenia or agranulocytosis. See Appendix 18.3 for a list of prohibited drugs.

### **6.4 Rescue Medication**

Rescue medication (intravenous administration of deferoxamine or combination of 2 iron chelators: deferiprone, deferoxamine or deferasirox) for the treatment of iron overload will not be allowed during the study. Should symptoms become intolerable for the patient, dose adjustment should be attempted. If the treatment is unsuccessful, the Investigator may decide to withdraw the patient from the study to optimize treatment.

### **6.5 Treatment Compliance**

Patients will be instructed on how to take the study medication. A medication usage diary card will be provided to the patients by the study staff. Patients will record the number of tablets or volume of oral solution taken, or the volume of injection solution administered and the time of injection. For deferiprone, compliance will be evaluated monthly by the Investigator or delegate by monthly pill counts or volume of drug returned by the patient. For deferoxamine, compliance will be evaluated by the number of infusions performed, which will be recorded monthly through the use of infusion pumps that keep records of those numbers, and by physical assessment of the infusion sites. Reasons for non-compliance with the treatment will be recorded in the source document and in the eCRFs. The Investigator should discuss treatment compliance with the patient and, if applicable, his/her parent or legal representative, at each visit.

Compliance reported in the eCRF will be based on the patient's diary and compliance calculation. If compliance is greater than 100% and the patient reports taking all doses as prescribed, compliance will be reported as 100% in the eCRF.

Compliance  $\leq 80\%$  and an over-compliance of  $\geq 120\%$  will be reported as a protocol deviation.

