### 9.1 Precautions/Overdose

An overdose is defined as taking more than the prescribed individual dose or more than maximum daily dose.

Deferiprone:

Deferiprone use can be associated with neutropenia, including agranulocytosis, the cause of which is currently unknown. Because of the awareness of this risk, weekly monitoring for neutrophil count was proposed in the first marketing authorization application for deferiprone and has been in effect since. However, a recent review of both clinical and post-marketing data accumulated over the last two decades confirmed that deferiprone-induced agranulocytosis is not dose-related within the therapeutic range, and its occurrence peaks at 5 months after initiation of therapy, declining in frequency after this period. It was concluded that weekly monitoring is a prudent approach but that it does not preclude agranulocytosis from occurring and it could even provide false security, as agranulocytosis could occur shortly after the finding of a normal neutrophil count. The relevance of weekly monitoring of the neutrophil count appears to decrease even further after the first six months of therapy, when agranulocytosis occurs less often. Based upon analysis of data collected over the past 20 years, it appears that patient education may be the key to minimizing risks associated with agranulocytosis during deferiprone therapy. A better approach to minimizing the risks in patients receiving long-term deferiprone therapy is for ANC monitoring to be done weekly only at the beginning of the treatment and to emphasize the importance of educating patients on the need to immediately stop deferiprone and to maintain ANC monitoring upon signs of infection.

Neurological disorders such as cerebellar symptoms, diplopia, lateral nystagmus, psychomotor slowdown, hand movements, and axial hypotonia have been observed in children who were treated with deferiprone at doses more than twice the maximum recommended dose of 100 mg/kg/day for transfusion-related iron overload for up to 16 months. The neurological disorders progressively regressed after deferiprone discontinuation.

Deferoxamine:

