Inadvertent administration of an overdose or inadvertent intravenous bolus administration/rapid intravenous infusion may be associated with hypotension, tachycardia, and gastrointestinal disturbances; acute but transient loss of vision, aphasia, agitation, headache, nausea, pallor, CNS depression including coma, bradycardia and acute renal failure have been reported. Acute respiratory distress syndrome has been reported following treatment with excessively high intravenous doses of deferoxamine in patients with acute iron intoxication and in patients with thalassemia.

Overdose per se will not be reported as an AE. The signs and symptoms or clinical sequelae resulting from overdose will be reported if they fulfill the AE or SAE definition.

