9 OTHER ANALYSES

9.1 Drug Exposure

The total daily dose taken during the study will be summarized with descriptive statistics by treatment group.

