9.2 Treatment compliance

Patients will be instructed on how to take the study medication. A medication usage diary card will be provided to the patients by the study staff. Patients will record the number of tablets or volume of oral solution taken, or the volume of injection solution administered and the time of injection. For Ferriprox, compliance will be evaluated monthly by the Investigator or delegate by monthly pill counts or volume of drug returned by the patient. For deferoxamine, compliance will be evaluated by the number of infusions performed, which will be recorded monthly through the use of infusion pumps that keep records of those numbers, and by physical assessment of the infusion sites. Reasons for non-compliance with the treatment will be recorded in the source document and in the eCRFs. Compliance reported in the eCRF will be based on the patient's diary and compliance calculation. If compliance is greater than 100% and the patient reports taking all doses as prescribed, compliance will be reported as 100% in the eCRF.

Compliance $\leq 80\%$ and an over-compliance of $\geq 120\%$ will be reported as a protocol deviation. The number and percent of patients who had compliance $\leq 80\%$ or $\geq 120\%$ during the study will be presented by treatment group.

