Pregnancy test: Positive		
Patient ID	XXXXXX XXXXXX XXXXXX XXXXXX	XXXXXX XXXXXX XXXXXX XXXXXX

Data source: 16.2.17 Listing of pregnancy

Table 14.3.8.1 The number and percent of patients who had compliance $\leq 80\%$ or $\geq 120\%$ during the study

	Treatment					
	Deferiprone		Deferoxamine		P-value (Fisher's exact test)	
Compliance	N	Percent	N	Percent		
$< 80\%$	xx	xx.x%	xx	xx.x%	0.xxxx	
$> 120\%$	xx	xx.x%	xx	xx.x%	0.xxxx	

Data source: 16.2.24 Listing of compliance

Table 14.5.1 Transfusional iron input (mg/kg/day) during the study

	Treatment					
	Deferiprone		Deferoxamine		P-value (T-test)	
	N	Mean \pm SD (Min, Max)	N	Mean \pm SD (Min, Max)		
Transfusional iron input (mg/kg/day)	xxx	xx.x \pm xx.x (xx, xx)	xxx	xx.x \pm xx.x (xx, xx)	0.xxxx	

Data source: 16.2.32 Listing of transfusion information

Table 14.6.1 Summary of total daily dose

	Treatment				
	Deferiprone		Deferoxamine		
	N	Mean \pm SD (Min, Max)	N	Mean \pm SD (Min, Max)	
Total daily dose (mg/kg/day)	xxx	xx.x \pm xx.x (xx, xx)	xxx	xx.x \pm xx.x (xx, xx)	

Data source: 16.2.22 Listing of dose verification

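### Replacing calculated compliance above 100% with 100% on the patient's report can mask over-compliance of 120% or more in the eCRF compliance field and in SAP Table 14.3.8.1

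*Protocol*

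**What the plan says.** Protocol 6.5 measures deferiprone compliance monthly by pill count or returned volume. Deferoxamine compliance is measured by the number of infusions recorded by the pump, with inspection of infusion sites. On what is entered, it says: "Compliance reported in the eCRF will be based on the patient's diary and compliance calculation". It then adds: "If compliance is greater than 100% and the patient reports taking all doses as prescribed, compliance will be reported as 100% in the eCRF". The following sentence says that compliance of 80% or less, or of 120% or more, "will be reported as a protocol deviation". SAP 9.2 repeats all of this and adds a summary by treatment group: "The number and percent of patients who had compliance" at or beyond either limit. The shell for that summary, Table 14.3.8.1, draws on the compliance listing (16.2.24) and compares the arms by Fisher's exact test.

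Three related provisions bear on whether excess intake would show elsewhere:

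- **Overdose.** Protocol 9.1 says: "An overdose is defined as taking more than the prescribed individual dose or more than maximum daily dose". It also says: "Overdose per se will not be reported as an AE". Signs, symptoms and sequelae remain reportable.
- **Dose taken, protocol.** Protocol 11.4.1.1 computes the number of doses taken from the dispensing and accountability eCRFs.
- **Dose taken, SAP.** SAP 9.1 says: "The total daily dose taken during the study will be summarized with descriptive statistics by treatment group". The shell for that table, 14.6.1, carries a different source: "Data source: 16.2.22 Listing of dose verification".

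**The concern.** The overwrite and the upper deviation limit stand next to each other, and the first can defeat the second. A pill count or returned volume is an objective measurement. Under the rule, a high result is replaced on the patient's word, while a low result always stands. A table meant to count patients at 120% or more is then built from a listing that, on the written rule, need not contain those values.

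The arms are unlikely to be affected equally. Tablets or solution that are lost, not returned or taken in excess all raise a pill or volume count. They have no counterpart in a count of infusions recorded by a pump. The comparison of arms in Table 14.3.8.1 could therefore understate over-compliance mainly on deferiprone.

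At stake is the accuracy of the compliance and exposure reporting. Overdose is not an adverse event by itself, so the over-compliance count is one of the few places where excess use would reach a summary table.

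**Working it through.** No power, sample size or alpha figure depends on this rule, so there is no stated figure to reproduce. The check is to apply the text as logic.

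**Inputs.** The overwrite rule and the 80% and 120% limits come from Protocol 6.5 and SAP 9.2. The daily doses, for scale, come from Protocol 6.2: 75 mg/kg/day initial and 99 mg/kg/day maximum.

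**Rule.** Reported = 100 if calculated > 100 and the patient reports all doses as prescribed; otherwise reported = calculated. The upper flag is raised if the value is ≥ 120.

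| Calculated (%) | Reported, patient says as prescribed | Flag on reported | Reported, patient does not say so | Flag on reported | Flag on calculated |
|---|---|---|---|---|---|
| 79 | 79 | no | 79 | no | no |
| 100 | 100 | no | 100 | no | no |
| 110 | 100 | no | 110 | no | no |
| 120 | 100 | no | 120 | yes | yes |
| 125 | 100 | no | 125 | yes | yes |
| 140 | 100 | no | 140 | yes | yes |

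Three results follow:

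1. If the patient reports dosing as prescribed, the reported value can never reach 120%, so the upper flag cannot be raised from it.
2. If the patient does not report this, the flag works as intended. The masking is conditional.
3. Values at or below 100% do not change. Applied to a single compliance value, the ≤ 80% deviation and the < 80% per-protocol exclusion are unaffected.

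**Scale.** 1.2 × 75 = 90 mg/kg/day and 1.2 × 99 = 118.8 mg/kg/day. At the higher dose the 120% limit lies above the maximum that the protocol states. This shows what a true 120% would mean; it does not show that anyone took it.

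**Which value drives the limit.** Neither document says whether the 120% test uses the calculated or the reported value. The compliance listing is the named source of Table 14.3.8.1, and nothing requires that listing to hold the calculated value.

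**Cut-offs.** SAP 9.2 and the title of Table 14.3.8.1 use ≤ 80% and ≥ 120%. The rows of the shell use < 80% and > 120%. A patient at exactly 80% or 120% is a deviation in the text and falls in neither row.

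**Dose taken.** Protocol 11.4.1.1 names dispensing and accountability data, while Table 14.6.1 names the dose-verification listing. The SAP does not define that listing. The visit activity of verifying and adjusting the dose level suggests that it holds the prescribed dose. If so, the table would not show excess intake. The SAP plans exposure listings for each drug (16.2.29 and 16.2.30), but no shell cites them.

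**The case against.** A reader might infer that overdosing disappears from the trial data. The documents do not support that:

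- The rule touches one eCRF field. Protocol 7.5 requires per-patient quantities dispensed and returned, and an explanation of missing tablets at the final inventory. The dispensing and accountability eCRFs and the exposure listings remain.
- The site does the count, reviews the diary and accounts for medication at its scheduled visits, and the monitor checks the eCRF against source. It cannot be said that nobody would see the excess.
- The diary records tablets or volume taken, not only a yes or no. A parent who gave too much in good faith would ordinarily write down the larger amount.
- A count above 100% is not proof of overdosing. Lost or unreturned drug gives the same result, and Protocol 7.4 provides for lost medication. Reconciling the count with the diary has a sensible purpose.

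A reader might also link the rule to the neurological disorders in children described in Protocol 9.1. Those occurred at more than twice the maximum dose, for up to 16 months. That is far from the 120% limit, and the sequelae of an overdose stay reportable.

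All of this stands, and it confines the point to compliance and exposure reporting. It does not remove the conflict. The surviving records do not feed Table 14.3.8.1, and the benign reading, that the deviation is judged on the calculated value, is not written down. A good reason for a high count calls for recording the reason beside the value, not for replacing the value.

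**Conclusion.** The point holds as a reporting defect. For patients who report dosing as prescribed, the rule as written can suppress the ≥ 120% deviation and understates the by-arm count in Table 14.3.8.1 if both are taken from the eCRF value. The documents do not give the frequency of calculated values above 100%, so the number of patients affected cannot be computed.

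The conclusion rests on these assumptions:

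- The compliance listing holds the reported value.
- The greater effect on deferiprone is an inference from the two methods of measurement; no figure in the documents shows it.
- The dose-verification listing holding the prescribed dose is likely but not stated.

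No effect on the primary ITT analysis is shown, because that analysis does not use compliance. The listed per-protocol exclusion for compliance is on the low side only, and no effect on it is shown either. The documents do not say how monthly values are combined into one figure per patient, so that last statement holds for the rule applied to a single value.

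**What to change.** 1. In Protocol 6.5 and SAP 9.2, replace the overwrite with an instruction to record the calculated compliance unaltered. Enter the patient's report and any explanation of lost or unreturned drug in separate fields.
2. State that the ≤ 80% and ≥ 120% deviations and Table 14.3.8.1 use the calculated value. For patients already finished or withdrawn (213 projected in the SAP by 30 November 2018), recalculate it from the accountability records.
3. Change the rows of Table 14.3.8.1 to ≤ 80% and ≥ 120%, to match the text and the table's own title.
4. Derive dose taken in Table 14.6.1 from the dispensing and accountability data through exposure listings 16.2.29 and 16.2.30, as Protocol 11.4.1.1 specifies, rather than from the dose-verification listing.

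The cost is a change to the eCRF fields and completion guidance, a few lines in the SAP, and a recalculation from records that the protocol already requires. The downside is that some lost or unreturned drug will appear as over-compliance; the explanation field identifies it.
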